Close monitoring remains essential to free tissue transfer success, and timing of intervention increases chance of successful salvage if problems arise. Previous studies in the plastic surgery literature have retrospectively analyzed data and determined certain tissue oxygenation patterns may exist in compromised skin flaps². However, these samples of data are in a very limited number of patients. Keller suggests that an absolute drop of StO₂ of 20% in an hour or an absolute StO₂ reading below 30% indicates flap compromise². This criteria may still produce false positives leading to patients returning to the OR without microvascular complication⁶.

The body of research on NIRS and non-invasive free flap monitoring has grown significantly in recent years. To our knowledge these studies have not been able to describe an inflection point or a specific pattern which characterizes the venous congestion curve. Identifying these specific patterns will help to establish an evidence-based approach in recognizing specific problems and patterns associated with tissue compromise that can guide physicians to consider earlier flap salvage measures.

Objectives

We hypothesize the rate of decline and pattern seen in tissue oxygenation as quantified by a NIRS device (ViOptiox T.Ox) can be quantified and described by a mathematical model which will allow earlier detection and identification of venous congestion in tissue. The vascular occlusion test has been established as a safe and accurate model to induce various states of vascular insufficiency and occlusion⁸⁻¹⁵. Specifically the vascular occlusion test has been demonstrated to be an accurate model for inducing venous insufficiency on awake and aware patients¹⁴. This study will aim to analyze the StO₂ data output of the ViOptiox in order to establish the earliest signs of tissue failure in various states of vascular compromise.

Methods and Measures

Design:

Subjects will be recruited through convenience sampling. Subjects will be given a study number at the initiation of the study and will not be identified through any identifying information throughout the study.

First, participants included will enter an examination room in the Department of Plastic and Reconstructive Surgery clinic. Subjects will be acclimatized for a minimum of 10 minutes before commencing the study. After 10 minutes of acclimatization, subjects will have their baseline vitals measured and recorded, including heart rate, temperature, blood pressure, height, weight, and BMI. Their blood pressure will be taken once on each arm to determine the baseline blood pressure. The variables to be measured and recorded will be pulse oximetry (SpO₂), transcutaneous oximetry (StO₂), demographic information, and past medical history.

The ViOptiox machine has the capability to measure two StO₂ values simultaneously. Two ViOptiox sensor probes will be secured to the subject, one over the volar forearm and one on the volar hand. The recording process on the ViOptiox machine will begin, and obtain baseline StO₂ levels for 5 minutes. After 5 minutes of baseline measurements the vascular occlusion test will be initiated. A blood pressure cuff will be inflated on one upper extremity in order to occlude venous outflow from the extremity. Venous

flow is reasonable occluded 20mmHg below systolic blood pressure. The cuff will thus not be inflated past the systolic pressure. This blood pressure cuff will be left inflated at a constant pressure for 10-20 minutes or as long as the subject can tolerate. Every 2 minutes a pulse check or doppler exam will be performed at the radial artery to ensure the arterial flow is present. For the duration of the vascular occlusion test the desired variables of SpO₂, StO₂ will be measured and recorded. The ViOptix machine continuously records StO₂ data. Every 2 minutes during the vascular occlusion test SpO₂ will be recorded. The cuff will be deflated and the subject will be free to leave the study room.

Setting:

The study will be conducted in a clinic room of the Department of Plastic and Reconstructive surgery. Subjects will include volunteers who meet inclusion/exclusion criteria and provide written informed consent for application of upper extremity tourniquet and monitoring by near infrared spectroscopy.

Subjects Selection Criteria

To be included in this study it is required that human subject participants are between 18 and 65 years of age and meet the following inclusion/exclusion criteria.

Inclusion Criteria

- Age 18 – 65 volunteers

Exclusion Criteria

- Subjects with a history of major cardiac disease, peripheral vascular disease including (vascular insufficiency), Raynaud syndrome, blood dyscrasias, pain syndromes, neurologic conditions, major upper extremity soft tissue trauma or previous vascular injury,

Sample Size

To ensure the study is adequately powered, we aim to include 40 subjects in the study. We will terminate data collection if 100 subjects undergo data collection process.

The number of subjects recruited has been determined by an a priori sample size calculation using the statistical software G*Power. Alpha will be set at 5% and beta at 20%. The necessary sample size will be determined based on previously collected data regarding the means and standard deviations of the measured variables, transcutaneous oximetry number in experimental and control conditions. Based on a previous pilot study we anticipate a large effect size in our data gathering. Given these previously researched values and effect size an early statistical sample size estimate using G*Power suggests a sample size of 32 subjects achieve statistical significance, however we will plan to enroll up to 40 subjects.

Interventions and Interactions

1. All identifying information will be removed from subject data collection forms
2. Anticipated data collection measures include but are not limited to age, gender, height, weight, BMI, vitals, O₂ saturation, TCOM, and past medical history.

The T.Ox™ device has 2 small monitors at the end of fiber optic cables that are placed on the skin of a patient. It is normally used after surgery to be placed on a patient directly on or near their surgical area to remain there for 48 hours post-operatively. For that intended use, The T.Ox™ sensor is packaged as a sterile device and is intended for single-use in a sterile environment. For this study however, the monitors are being placed on the wrists of patients with no surgical interventions. The monitors will remain on for only the length of the study visit (~35min) as opposed to 48 hours after a surgery.

Because this is a non-significant risk study for non-invasive data collection only, we plan to re-use the sterile T.Ox™ sensor on multiple subjects with appropriate cleaning (Sani Cloth AF3 wipe) between uses as with any non-sterile device used on multiple subjects. The device will be allowed to dry for 3 minutes per instructions. This wipe has shown effectiveness against SARS-CoV-2.

Outcome Measures

We will collect de-identified data including age, gender, BMI. WE will collect vital signs prior to initiation of vascular occlusion test. Additionally, we will collect tissue oxygenation values from the ViOptix terminal, and oxygen saturation via pulse oximetry. The main outcome measure will be the change in StO2 over time of vascular occlusion test.

Analytical Plan

We will initially use descriptive statistics to quantify and describe the results. We will aim to analyze the rate of change of tissue oxygenation across time to better define the aggregate rate of change. We will use descriptive statistics to compare subject demographic data.

Human Subjects Protection

There will be no identifying subject information included in data collection. Informed consent will be required prior to enrollment and initiation of the study. Subjects will be provided informed consent and given the option to participate in the study or decline. All data will be de-identified and there will be no way to link data collection to specific subject. Subjects and characteristics will be identified by a generated code for database codification.

Subject Recruitment Methods

Subjects for the study will be recruited via convenience sampling. A minimum of 32 subjects at WFBMC will be recruited for the study. A face to face interaction will occur in the exam room where the potential subject will have the opportunity undergo the informed consent process and decide to participate in the study. If they agree to participate the subject will be enrolled and will proceed with data collection after informed consent is obtained.

Informed Consent

Signed informed consent will be obtained from each subject. Informed consent will be obtained after the study has been fully explained to each subject and all questions and concerns have been properly addressed. The investigators or a member of the study team will obtain informed consent. Informed consent will take place in a private examination area of Plastic and Reconstructive Surgery clinical areas. After signing the ICF, the subject will be given a signed copy.

Confidentiality and Privacy

Confidentiality will be protected by collecting only de-identified information needed to assess study outcomes, thus any information that could directly identify subjects. The de-identified database will be kept in a secure excel file on the Plastic Surgery Drive on the WFBMC network. Identities will not be saved on data collection forms. We will be producing an anonymous analytical data set. Data access will be limited to study staff. Data and records will be kept locked and secured, with any computer data password protected. No reference to any individual participant will appear in reports, presentations, or publications that may arise from the study. The planned data to be collected will not include any of the 18 personal identifiers set forth by HIPAA.

Data and Safety Monitoring

The principal investigator will be responsible for the overall monitoring of the data and safety of study participants. The principal investigator will be assisted by other members of the study staff.

Reporting Unanticipated Problems, Adverse, Events, or Deviations

Any unanticipated problems, serious and unexpected adverse events, deviations or protocol changes will be promptly reported by the principal investigator or designated member of the research team to the IRB and sponsor or appropriate government agency if appropriate.

References:

- 1 Keller A. Non-invasive tissue oximetry for flap monitoring: An initial study. *J Reconstr Microsurg* 2007;**23**:189–97. <https://doi.org/10.1055/s-2007-974655>.
- 2 Keller A. A new diagnostic algorithm for early prediction of vascular compromise in 208 microsurgical flaps using tissue oxygen saturation measurements. *Ann Plast Surg* 2009;**62**:538–43. <https://doi.org/10.1097/SAP.0b013e3181a47ce8>.

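### The protocol hypothesises earlier detection of venous congestion, but the Analytical Plan applies no reference rule to the traces, so a statement that a new sign is earlier would be unsupported

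*Combined protocol and SAP*

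**What the plan says.** The comparative aim is in the opening text and the Objectives. The hypothesis is that a model of the StO2 decline can be found "which will allow earlier detection and identification of venous congestion in tissue". The study is to "establish the earliest signs of tissue failure in various states of vascular compromise", and the background hopes for patterns "that can guide physicians to consider earlier flap salvage measures".

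The background also gives the only numerical rule in the document, credited to one cited study that suggests it: an absolute StO2 drop "of 20% in an hour or an absolute" StO2 "reading below 30% indicates flap compromise". It then notes a weakness: "This criteria may still produce false positives leading to patients returning to the OR without microvascular complication".

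Under Design, StO2 is recorded continuously at two sites, forearm and hand. "After 5 minutes of baseline measurements the vascular occlusion test will be initiated". The cuff then stays inflated for 10-20 minutes or for as long as the subject tolerates it.

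Outcome Measures names one main outcome, the change in StO2 over the occlusion test. On StO2, the Analytical Plan offers initial descriptive statistics and this: "We will aim to analyze the rate of change of tissue oxygenation across time to better define the aggregate rate of change". The cited criterion does not appear after the background. No detection rule, time to detection or lead time is defined anywhere.

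**The concern.** *Earlier* is a comparative and needs something to be earlier than. The document supplies a candidate and records the data on which to try it, but does not plan to do so. Followed as written, the trial ends with an average slope, perhaps with a described curve or inflection. A reader could not tell whether the cited criterion would have been met sooner, later or not at all on the same traces. What is at stake is the claim most likely to be carried into flap monitoring, not the description of the curve itself.

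**Working it through.** **1. Does any planned analysis supply a reference?** The main outcome is a change over time, and the analysis target is an aggregate rate. Neither is a time to an event. Sample Size gives 32 subjects (alpha 5%, beta 20%, large effect) for oximetry in experimental versus control conditions, not for a new sign against an existing rule. The figure cannot be reproduced uniquely, because no test, sidedness or numerical effect is stated. A conventional large effect of d = 0.8, two-sided, gives 15 subjects for a paired t-test or 52 in total for two independent groups. A chi-square test with w = 0.5 and 1 df does give 32. None of these bears on *earlier*.

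**2. Could the cited criterion be met within the test?** Inputs: a drop of 20, read as absolute StO2 points, and the below-30% limit (background); 10 to 20 minutes of occlusion (Design). Slope s in points/min and baseline B are assumptions, because the documents give neither. For a linear fall:

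- Slope needed for the drop limb: 20/10 = 2.0 points/min within 10 minutes; 20/20 = 1.0 point/min within 20 minutes.
- The below-30% limb needs a fall of just over B - 30. This is less than 20 when B is below 50, so that limb then comes first.
- For B above 30, time to criterion is therefore about min(20, B - 30)/s.

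| Assumed s (points/min) | B of 50 or more: 20/s | B = 40: 10/s |
|---|---|---|
| 0.5 | 40 min | 20 min |
| 1.0 | 20 min | 10 min |
| 2.0 | 10 min | 5 min |
| 3.0 | 6.7 min | 3.3 min |

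Over this range the criterion is met anywhere from a few minutes after inflation to well beyond deflation. Whether a new sign would be earlier, and by how much, cannot be presumed.

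**3. What does not meeting the criterion mean?** Baseline plus occlusion is at most 5 + 20 = 25 minutes if the stated range is kept, and the visit lasts about 35 minutes (Interventions and Interactions). A 20-point fall inside the test is also a 20-point fall inside an hour, so a positive is valid. A trace that has not met the criterion at deflation is censored; it is not a miss.

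**4. What precision would a paired comparison have?** If both rules were met in every subject, a two-sided 5% paired t-test has 80% power for a mean lead time of 0.45 SD with 40 subjects, or 0.51 SD with 32. Censoring reduces this. No SD is given, so minutes cannot be stated.

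**5. Can the baseline support a false-alarm comparison?** Unoccluded time per probe site is 40 x 5/60 = 3.3 hours. With zero alarms and a constant rate, the one-sided 95% upper bound is -ln(0.05)/3.33 = 0.90 per hour, or 0.90 x 48 = about 43 over the 48 hours for which the device is normally worn. The drop limb would also be tested on the same 5 minutes that define its baseline, so it would rarely be met, almost by construction.

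**The case against.** The strongest reply is that this is a first-stage descriptive study. The gap the background names is that no one has described an inflection or pattern for the venous congestion curve, and describing it needs no alarm comparator. StO2 is recorded continuously and the plan says its analysis is *initially* descriptive, so the criterion could be applied later. This stands as far as the main outcome goes, and it limits the severity. It does not supply a basis for *earlier*, and a comparison chosen after the curves have been seen is weaker than one written down now.

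A second reply is that the comparison could favour the new sign. No new sign is defined, and one tuned and tested on the same traces, with known inflation time, could easily beat a 20-point threshold. This is correct, and the fix has to deal with it.

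Three stronger readings are tempting, and the documents support none of them:

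- A reader might infer that the protocol promises earlier detection, or that the cited criterion is the standard rule in use. The text hypothesises the first and says only that one study suggests the second.
- A reader might infer that the 5-minute baselines could show whether a new sign gives fewer false alarms. Step 5 shows that they could not. The false positives in the background are returns to theatre without a microvascular complication, which volunteers with intact limbs cannot show.
- A reader might take the 40-minute entry in the table as a likely lead time of 20 minutes or more. It rests on an assumed 0.5 point/min, a linear fall and a baseline of at least 50.

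**Conclusion.** The gap is real but limited. The plan can deliver its descriptive outcome. It cannot support a statement that a new sign is earlier, because it applies no reference to the traces. The size of any lead time is unknown and cannot be derived from the documents. What can be said is that the drop limb falls inside the test only at average slopes of 1.0 to 2.0 points/min or more, depending on the occlusion time, and that the below-30% limb can come first when baseline is below 50. This assumes that the 20% drop means 20 absolute points and that the fall is linear. Even with the comparison added, the conclusion would cover healthy limbs over 10-20 minutes, not flaps, and would say nothing about relative false-alarm rates. The plan should be changed before the traces are analysed.

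**What to change.** Add to the Analytical Plan:

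1. For each subject and probe site, the first time after inflation at which StO2 is 20 points below that subject's 5-minute baseline mean or below 30%, censored at deflation. Report the proportion reaching it and a Kaplan-Meier time to criterion, with the sites shown separately. Because the cuff may come down early for intolerance, also report deflation times and reasons.
2. If a new rate or inflection sign is proposed, fix its rule before the comparison or evaluate it by leave-one-subject-out cross-validation. Then report the paired lead time (criterion time minus sign time), as a lower bound where the criterion is censored, and the number of subjects in whom the sign is not met.
3. Limit any statement of *earlier* to this comparison in healthy limbs over 10-20 minutes, or drop the word.
4. Make no comparative false-alarm claim.

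This is an analysis rule only; it does not propose an alarm for clinical use. It needs no new subjects, visits or measurements, though inflation and deflation times must be marked on each trace, which the protocol does not mention. The cost is a short addition to the plan, plus the cross-validation if a sign is derived from these data. The downside is that many traces may be censored, leaving only lower bounds on lead time.

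### The Analytical Plan names only an aggregate rate of StO2 change, but detecting congestion in one patient also needs the spread between subjects and the overlap with unoccluded rates

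*Combined protocol and SAP*

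**What the plan says.** The Objectives section states the hypothesis that the rate and pattern of StO2 decline "can be quantified and described by a mathematical model which will allow earlier detection and identification of venous congestion in tissue". The background before it says that such patterns should help identify "problems and patterns associated with tissue compromise that can guide physicians to consider earlier flap salvage measures". It faults an existing rule (an absolute StO2 drop of 20% in an hour, or a reading below 30%) because "This criteria may still produce false positives leading to patients returning to the OR without microvascular complication". Salvage decisions and false positives both concern single patients.

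Under Outcome Measures, "The main outcome measure will be the change in StO2 over time of vascular occlusion test". The Analytical Plan has three sentences. It opens with "We will initially use descriptive statistics to quantify and describe the results", continues with "We will aim to analyze the rate of change of tissue oxygenation across time to better define the aggregate rate of change", and ends with a descriptive comparison of demographics. For the rate it names no between-subject SD, percentile, prediction or tolerance interval, per-subject slope, cut-off, sensitivity or specificity.

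The Design text gives what a subject-level analysis would need: continuous StO2 recording, two probes (forearm and hand), a 5-minute baseline, and then cuff inflation for 10-20 minutes or for as long as it is tolerated.

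**The concern.** The stated purpose and the stated estimate are at different levels. Recognising congestion in one monitored patient requires knowing how slowly StO2 can fall in a limb that really is occluded, and how fast it can drift in one that is not. An aggregate rate answers neither question. It locates the average occluded limb, and its precision improves with sample size while the variation between people stays the same.

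If curves are pooled or averaged before a rate is taken, the between-subject spread of rates is lost from the results. Because tolerated cuff time varies, rates taken over each subject's own duration would also mix windows of different length. The study could then report a tight mean and still be unable to say whether a rate-based warning is feasible, which is what the hypothesis is about.

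**Working it through.** **Plan's own figures.** The documents state no cut-off, miss rate, mean rate or SD, so there is nothing on this point to reproduce. The Sample Size section gives 32 subjects, with up to 40 planned ("Alpha will be set at 5% and beta at 20" per cent). Without a named test and a numeric effect size, 32 can be neither confirmed nor refuted. That is a separate matter and does not enter below.

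**Inputs.** n = 32 and n = 40 come from Sample Size. Rates are expressed in units of the between-subject SD, or as a share of the mean for an assumed coefficient of variation (CV). The CVs are my assumption.

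**1. Precision of the mean against one new subject** (normal rates).
- 95% CI half-width for the mean = t(0.975, n−1)/√n. For n = 40: 2.023/6.325 = 0.32 SD. For n = 32: 2.040/5.657 = 0.36 SD.
- 95% prediction half-width for one subject = t × √(1 + 1/n). For n = 40: 2.023 × 1.0124 = 2.05 SD. For n = 32: 2.040 × 1.0155 = 2.07 SD.
- Ratio at n = 40: 2.05/0.32 = 6.4.

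**2. Illustration: a cut-off placed at the mean.** The share of occluded subjects falling more slowly than the cut-off is Φ(0) = 50% for any symmetric distribution, whatever the SD. For right-skewed (lognormal) rates it is Φ(√ln(1 + CV²)/2), which gives 52%, 55% and 59% at CV 10%, 25% and 50%. The mirror-image left skew gives 48%, 45% and 41%. When the mean is itself estimated from 40 subjects, simulation (200,000 replicates, normal rates) gives an average of 50%, with a 95% range of 38% to 62%.

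**3. What the spread adds.** In the same simulation, a cut-off at the estimated mean minus 1.645 estimated SD misses 5.6% on average at n = 40 (95% range 1.7% to 12.2%) and 5.8% at n = 32 (1.5% to 13.5%).

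**4. Lower limits as a share of the mean** (normal rates, n = 40). The 5th percentile is 1 − 1.645 × CV. The one-sided 95%/95% tolerance limit is 1 − k × CV, where k is the 95th percentile of the noncentral t distribution (n−1 df, noncentrality 1.645√n) divided by √n. This gives k = 2.13 at n = 40 and 2.20 at n = 32.

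| Assumed CV | 5th percentile | 95%/95% limit, n = 40 |
|---|---|---|
| 20% | 67% | 57% |
| 33% | 46% | 30% |
| 50% | 18% | −6% |

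The normal 95%/95% limit reaches zero at CV = 1/2.13 = 47%. The normal 5th percentile does so only at 1/1.645 = 61%, and a 90%/95% limit (k = 1.70 at n = 40) at 1/1.70 = 59%. With lognormal rates at CV 50%, the log-scale SD is √ln(1.25) = 0.472 and the 95%/95% limit is exp(−0.472²/2 − 2.13 × 0.472) = 33% of the mean. The limit therefore depends heavily on the distributional assumption.

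**5. False alarms.** Steps 2 to 4 use occluded subjects only. False alarms depend on how far those rates overlap with unoccluded ones. The only unoccluded data planned are the 5-minute baselines.

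**The case against.** The strongest reply is that the plan contains no detection rule. No cut-off or alarm is set at the mean rate, so a reader might infer from step 2 that the trial has a 50% miss rate. It does not: that figure is a property of any symmetric distribution cut at its mean and uses no trial data. This objection stands, and the figure is kept only as an illustration.

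A second reply is that the study describes the venous congestion curve in volunteers, and that a single-patient limit belongs to later work. This stands in part. The study need not validate a limit, but describing a curve for later use in detection includes describing how much it varies between people. The points below also leave the inflection point and the mathematical model to be specified separately.

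A third reply is that descriptive statistics ordinarily include an SD, and that the word aggregate is not defined and might mean overall across the test. The plan does not exclude spread. It does not commit to it either, and it neither requires one rate per subject nor links any spread to detection.

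Finally, a limit from occluded subjects alone addresses misses and ignores false alarms, which are the weakness the background names in the existing rule. This stands, and the fix therefore uses the baseline as well.

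**Conclusion.** The concern holds as a mismatch between purpose and analysis. The aim is recognition of congestion in a single patient. The only rate estimate named is a group one, and at n = 40 its confidence interval is more than six times narrower than the range for one new subject. That comparison assumes roughly normal rates and does not depend on the unknown SD.

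Two stronger readings are not supported. The plan does not adopt a rule that misses half of occluded subjects, because it adopts no rule. Nor does a between-subject CV above 47% mean that no decline-rate cut-off could work: only the normal 95%/95% limit at n = 40 reaches zero there, other limits stay positive beyond it, and usefulness depends on overlap with unoccluded rates. The actual CV is not in the documents, so the size of the problem in this trial is unknown until the spread is reported. The change is worth making, and nothing in data collection has to be altered.

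**What to change.** Add to the Analytical Plan:

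- For each subject, and for forearm and hand separately, compute the StO2 rate of change over one common post-inflation window fixed in advance, for example the first 10 minutes. Subjects who stop earlier are analysed over their available time and flagged.
- Compute the same rate over each subject's 5-minute baseline.
- By site, report mean, SD, median, 5th and 10th percentiles with confidence intervals, the individual curves, and the overlap between occluded and baseline rates. With 40 subjects the lowest observation falls below the true 5th percentile with probability 1 − 0.95^40 = 0.87, so a 95% lower confidence bound for that percentile needs a distributional model. For the 10th percentile the figure is 1 − 0.90^40 = 0.985, so a distribution-free bound is available.
- Optionally, as exploratory, add a one-sided 95%/95% normal tolerance limit (k = 2.13 at n = 40, 2.20 at n = 32) after checking normality or transforming.
- State that the aggregate rate is descriptive and is not itself a detection threshold.

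The cost is a few lines of text and slightly more analysis of data already recorded. The downsides are a limit that will look less favourable than the mean, and a short baseline that makes the unoccluded rates noisy, so the overlap should be presented as a preliminary estimate.
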